- High Blood Pressure	Medical history of uncontrolled high blood pressure is defined as a deficient standard of care treatment or blood pressure > 140/90 mm/Hg during the screening visit in a patient taking anti-hypertensive treatment. At screening, all patients must have a blood pressure < 140/90 mm/Hg.
- Other diseases	Medical history of inherited thrombophilias, cancer of the lung, brain, lymphatic, gynecologic system (ovary or uterus), or gastrointestinal tract (like pancreas or stomach).
- Other conditions	Lower extremity paralysis due to spinal cord injury, fracture of the pelvis, hips or femur or recent major general surgery (within 12 months before the Screening).

8. Study participant has received any stem cell treatment within 12 months before the first dose of the investigational product other than stem cells produced by Hope Biosciences.
9. The study participant has received an experimental drug within 12 months before the first dose of the investigational product. (Except for COVID-19 vaccinations)
10. Study participant has a laboratory abnormality during screening, including the following:
 - White blood cell count WBC \leq 3.0 K/UL and \geq 12.0 K/UL
 - Platelet count \leq 80 K/UL and or \geq 450 K/UL
 - Absolute neutrophil count \leq 1.50 K/UL and or \geq 7.50 K/UL
 - Alanine aminotransferase (ALT) of > 75 U/L
 - Aspartate aminotransferase (AST) of > 75 U/L
 - Hemoglobin (Hgb) <11 G/DL or >18 G/DL
 - Hematocrit (HCT) <33% or >54 %
 - Mean corpuscular volume (MCV) < 75 FL or >100 FL
 - Mean corpuscular hemoglobin (MCH) <23 PG or >36 PG
 - Mean corpuscular hemoglobin concentration (MCHC) <30 G/DL or > 37gG/DL
 - Red cell distribution width (RDW) < 10% or >14%
 - Abnormal laboratory results considered clinically significant by the principal investigator will exclude patients from participation in this investigation. See annexes for laboratory normal values.

11. The study participant has any known ongoing infection, including but not limited to TB, CMV, EBV, HSV, VZV, hepatitis virus, toxoplasmosis, HIV, syphilis infections, hepatitis B surface antigen-positive, or hepatitis C PCR positivity.
12. The study participant is unlikely to complete the study or adhere to the study procedures.
13. The study participant has a previously diagnosed psychiatric condition that may affect self-assessments in the investigator's opinion.

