Vital signs will be measured at Visits 1, 2, 3, 4, 5, 6, 7 and 8. Study personnel will measure respiratory rate (breaths per minute), pulse rate (beats per minute), blood pressure (mmHg) (measured after the study participant has been seated for more than 5 minutes of rest), body temperature (F), and oxygen saturation (%). The principal investigator must evaluate the clinical significance of any abnormal result. Clinically significant abnormal findings will be reported as adverse events.

Clinical Safety Laboratory Parameters

The following laboratory parameters should be collected at Visit 1, 2, 5, and 8.

- Comprehensive Metabolic Panel, also known as CMP or Chemistry Panel, is a group of different tests that measure several substances in the study's participant blood. The following tests are included in this panel:

Comprehensive Metabolic Panel (CMP)	Reference Range	Units
GLUCOSE	70-99	MG/DL
BUN	6-20	MG/DL
CREATININE	0.60-1.30	MG/DL
eGFR AFRICAN AMER.	>60	ML/MIN/1.73
eGFR NON-AFRICAN AMER.	>60	ML/MIN/1.73
CALC BUN/CREAT	6-28	Ratio
SODIUM	133-146	MEQ/L
POTASSIUM	3.5-5.4	MEQ/L
CHLORIDE	95-107	MEQ/L
CARBON DIOXIDE	19-31	MEQ/L
CALCIUM	8.5-10.5	MG/DL
PROTEIN, TOTAL	6.1-8.3	G/DL
ALBUMIN	3.5-5.2	G/DL
CALC GLOBULIN	1.9-3.7	G/DL
CALC A/G RATIO	1.0-2.6	Ratio
BILIRUBIN, TOTAL	<=1.2	MG/DL
ALKALINE PHOSPHATASE	40-114	U/L
AST	9-40	U/L
ALT	5-40	U/L

- Complete Blood Count, also known as CBC, hemogram, or CBC with Differential, is a group of tests that evaluate the cells circulating in the blood. The following tests are included in this panel:

CBC with manual differential	Reference Range	Units
WBC	3.5-11.0	K/UL
RBC	3.80-5.40	M/UL
HEMOGLOBIN	11.5-15.5	G/DL
HEMATOCRIT	34.0-45.0	%
MCV	80.0-99.0	fL
MCH	25.0-33.0	PG
MCHC	31.0-36.0	G/DL
RDW	11.5-15.0	%
NEUTROPHILS	40.0-75.0	%
LYMPHOCYTES	20.0-45.0	%
MONOCYTES	4.0-12.0	%
EOSINOPHILS	0.0-7.0	%
BASOPHILS	0.0-2.0	%
PLATELET COUNT	130-400	K/UL
ABSOLUTE NEUTROPHILS	1.50-7.50	K/UL
ABSOLUTE LYMPHOCYTES	1.00-4.00	K/UL
ABSOLUTE MONOCYTES	0.20-1.00	K/UL
ABSOLUTE EOSINOPHILS	0.00-0.50	K/UL
ABSOLUTE BASOPHILS	0.00-0.20	K/UL

- Coagulation Tests including Prothrombin Time (PT, PTT-INR) to identify any coagulation disorder during study participation.

Coagulation	Reference Range	Units
Prothrombin Time (PT)	12.5-14.7	Seconds
INR	2.0-3.0	N/A
Partial thromboplastin time (PTT)	25.2-40.0	Seconds

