5.3.2.3. Clinical Laboratory data

Laboratory evaluations including CBC- complete blood count, CMP- comprehensive metabolic panel and Coagulation Panel. The details of the planned displays are in programming specification document.

All laboratory parameters, including numerical urine analysis parameters will be summarised descriptively. Categorical urine analysis results will be summarized using count and percentage based on subjects.

Results of urine pregnancy test will be listed in individual subject data listings only.

Individual laboratory evaluations will be listed. In addition, a listing containing individual subject laboratory values outside the normal reference ranges will be provided.

Data recorded at unscheduled assessments will not be included in tables and figures but will be listed.

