7.2. Appendix 2 Data Derivation Rule

7.2.1. Criteria for Potential Clinical Importance

The potential clinical importance criteria are not defined this trial. A laboratory value that is outside the reference range is considered either high abnormal or low abnormal will be displayed based on lab normal range data.

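### The protocol's INR reference range of 2.0–3.0 contradicts the PT range beside it: no sample can be normal on both rows

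*Protocol*

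**What the plan says.** Protocol, Clinical Safety Laboratory Parameters: the coagulation panel is described as "Coagulation Tests including Prothrombin Time (PT, PTT-INR) to identify any coagulation disorder during study participation". Its table has a reference-range column that reads "Prothrombin Time (PT) 12.5-14.7 Seconds", then 2.0–3.0 for INR, then 25.2–40.0 seconds for PTT. The same section sets the timing: "The following laboratory parameters should be collected at Visit 1, 2, 5, and 8". No other INR range appears in the documents supplied.

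Protocol, Investigational Plan: the screening laboratory results are used to decide eligibility. Exclusion criterion 10 gives numeric limits for blood counts, red-cell indices, ALT and AST, but none for PT, INR or PTT. For everything else it says: "Abnormal laboratory results considered clinically significant by the principal investigator will exclude patients from participation in this investigation. See annexes for laboratory normal values".

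Protocol, Primary Endpoints: changes in laboratory values are listed among the primary safety endpoints.

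SAP 5.3.2.3: laboratory parameters are summarised descriptively and individual evaluations are listed. In addition, "a listing containing individual subject laboratory values outside the normal reference ranges will be provided". SAP 7.2.1 defines the flag: "A laboratory value that is outside the reference range is considered either high abnormal or low abnormal will be displayed based on lab normal range". The SAP does not say whether the laboratory range file behind this flag takes its limits from the protocol table or from the laboratory.

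**The concern.** INR is a standardised form of PT, so the two rows of the table describe one measurement on one sample. A person whose PT is normal should also have a normal INR. With 2.0–3.0 printed as the INR reference range, that person reads as low, while someone whose INR has risen to 2–3 reads as in range. On that row the flag is inverted.

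The panel is there to find coagulation disorders, and aspirin is listed among the medications before each infusion. A raised INR means slower clotting, so bleeding is the relevant risk. There is no numeric coagulation exclusion to act as a backstop at screening. If the same range reached the SAP's range file, the INR part of the abnormal-value listing would consist of normal samples marked low and would leave out samples with an INR of 2–3.

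**Working it through.** **Inputs from the documents.** PT reference range 12.5–14.7 s and INR reference range 2.0–3.0 (Protocol, coagulation table). Planned enrolment is 80. The panel is drawn at Visits 1, 2, 5 and 8.

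**Inputs assumed.** The documents give neither the mean normal PT (MNPT) nor the ISI. I take MNPT from 12.5 to 14.7 s (central 13.6 s, the midpoint) and ISI from 0.8 to 2.5 (central 1.0).

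**Formula.** INR = (PT / MNPT)^ISI.

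**Step 1: can the PT range reproduce the listed INR range?**

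| MNPT (s) | ISI | INR at PT 12.5 s | INR at PT 14.7 s |
|---|---|---|---|
| 13.6 | 1.0 | 12.5/13.6 = 0.92 | 14.7/13.6 = 1.08 |
| 13.6 | 1.5 | 0.919^1.5 = 0.88 | 1.081^1.5 = 1.12 |
| 12.5 | 2.0 | 1.00 | 1.176^2.0 = 1.38 |
| 12.5 | 2.5 | 1.00 | 1.176^2.5 = 1.50 |
| 14.7 | 2.5 | 0.850^2.5 = 0.67 | 1.00 |

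Over the whole grid the INR lies between 0.67 and 1.50. It never reaches 2.0, so the listed INR range is not reproduced.

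**Step 2: what would make the rows agree?** For a PT of 14.7 s to give an INR of 2.0, ISI must equal ln 2 / ln(14.7/MNPT). That is 4.3 at MNPT 12.5 s and 8.9 at MNPT 13.6 s, both outside the assumed range.

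**Step 3: what PT goes with an INR of 2–3?** PT = MNPT × INR^(1/ISI). At the central values this gives 13.6 × 2 = 27.2 s and 13.6 × 3 = 40.8 s. The lowest PT on the grid that gives an INR of 2.0 is 12.5 × 2^(1/2.5) = 16.5 s. Even that is above the 14.7 s limit, so every sample with an INR of 2–3 is high on the PT row.

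**Step 4: how many samples could be mis-flagged?** If the range file holds 2.0–3.0, every normal-PT sample is marked low on INR. With 80 participants and three samples each (Visits 2, 5 and 8), the ceiling is 80 × 3 = 240, plus screening samples. The Handling of Biological Samples section words the early draw as Visit 1 or Visit 2. On that reading the firm count is Visits 5 and 8, 80 × 2 = 160, plus one early sample each. If the file holds the laboratory's own interval, the protocol's row causes no wrong flags.

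**The case against.** The two rows plainly disagree, but a case can be made that little follows from it. Most of that case stands.

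- **Missed coagulopathy.** A reader might infer that a candidate or participant with an INR of 2–3 would go unnoticed. The documents do not support this, because the PT row from the same panel would be out of range high (Step 3). The masking is confined to the INR row.
- **Automatic eligibility.** A reader might infer that such a candidate passes screening. Exclusion 10 has no coagulation limit to pass or fail. It relies on the investigator's view of clinical significance and on annexes that were not supplied, and the Case Report Forms section has the investigator mark significant values on signed reports. Nor do the tabulated ranges decide eligibility: exclusion 10 uses platelet limits of 80 and 450 against a reference range of 130–400.
- **Loss of the endpoint.** A reader might infer that INR drops out as a safety measure. It does not. The descriptive summaries and individual listings in SAP 5.3.2.3 use no reference range, so a rise from about 1 to 2.5 would still be visible.
- **Certain mis-flagging.** SAP 7.2.1 works from laboratory range data, which may hold the correct interval.
- **Thrombosis.** Missing a raised INR bears on bleeding more than on the thromboembolic events of special interest. Thrombotic risk is covered separately in exclusions 7 and 16.

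What remains is the table itself. Anyone using the only INR range in the documents gets opposite readings from two rows for one sample, and nothing says which source governs the flags.

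**Conclusion.** The INR row is wrong as written beside the PT row. Under every assumed mean normal PT (12.5–14.7 s) and ISI (0.8–2.5), a PT in range gives an INR of at most about 1.5, so no sample is normal on both rows. This rests on the definition of INR and on a mean normal PT that lies inside the laboratory's own PT range.

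The consequences are conditional. The SAP's INR flags and out-of-range listing would be wrong for every normal-PT sample, up to 240 after screening, only if the protocol's range is in the range file. At screening the effect runs only through the investigator's judgement. This is a should-fix correction to a safety table. It affects no efficacy analysis, alpha or sample size.

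**What to change.** 1. In the protocol's coagulation table, reconcile the INR row with the PT row by using the testing laboratory's own reference interval. The figure must come from that laboratory. The values in the working only show the contradiction and are not a proposed range.
2. In SAP 5.3.2.3 and 7.2.1, state that the laboratory's interval is the source for the high/low flags and the out-of-range listing.
3. Check that the laboratory range file and the annexes cited in exclusion 10 carry the same interval.
4. Re-read any coagulation results already judged against 2.0–3.0, including those at screening.

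The cost is one table row in a protocol amendment, one sentence in the SAP, a check of the range file, and possibly a second look at a few results.

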The FAS is a ten-item scale that assesses the symptoms of chronic fatigue in an individual. The FAS considers fatigue as a unidimensional concept rather than a collection of variables that may be measured separately. Additionally, to guarantee that the scale would assess all elements of fatigue, the scale's developers included questions that represented both physical and mental symptoms of the disease (Michielsen et al., 2004).

Short Form Questionnaire – 36

The SF-36 is a multi-purpose survey intended to collect adult patients' views of their health and well-being. In all, there are 36 questions on the SF-36, which are organized into eight dimensions: physical functioning, physical and emotional limitations, social functioning, physiological discomfort, general and mental health. It is a more public health measure than targeted at a particular age group, illness, or treatment group. This questionnaire may be given in various situations (e.g., primary care, community clinics, specialty care serving patients with chronic conditions). It has been extensively utilized and proved helpful in multiple studies of general and populations throughout the years, including evaluating the relative burden of illnesses and differentiating the health benefits provided by a range of various therapies (National Center for Interprofessional Practice and Education, 2016).

Physical Examinations

The principal investigator or delegated sub-investigator will perform a complete physical examination. This exam will include general appearance, head, eyes, ear, nose, and throat (HEENT), neck, cardiovascular, thorax/lungs, abdomen, genitourinary, musculoskeletal, lymph nodes, skin, neurological and mental status examination, height (at Screening only), and body weight at Visits 1, 2, 3, 4, 5, 6, 7 and 8.

The principal investigator or delegated sub-investigator will evaluate the clinical significance of abnormal findings identified during physical examinations. Pre-existing conditions diagnosed through assessments and examinations at the screening visit or during the screening period are not adverse events but are recorded as medical history. If any clinically significant abnormal findings are

discovered after informed consent or any pre-existing conditions worsen during the trial, these must be recorded as adverse events.

Vital Signs

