Sampling tubes, material for shipments of the samples, and a laboratory manual detailing all sample collection and shipment procedures will be provided and distributed to the clinical trial site by the selected laboratory. Laboratory samples will be collected as per protocol during Visit 1 – Screening or Visit 2 – Infusion 1 (Baseline), Visit 5 – Infusion 4, and Visit 8 - End of Study.

Adverse Events

Unanticipated Problems Involving Risk to Subjects or Others

Any incident, experience, or outcome that meets all the following criteria:

- Unexpected in nature, severity, or frequency (i.e., not described in study-related documents such as the IRB-approved protocol or consent form, the investigator's brochure, etc.)
- Related or possibly related to participation in the research (i.e., perhaps related means there is a reasonable possibility that the incident experience or outcome may have been caused by the procedures involved in the study.
- Serious (as defined below) ***“Serious” is different than “severe” as reported in the CTC criteria that apply a grade to the AE.***

Adverse Event

An **adverse event** (AE) is any symptom, sign, illness, or experience that develops or worsens in severity during the study. Intercurrent illnesses or injuries should be regarded as adverse events.

Abnormal results of diagnostic procedures are adverse events if the abnormality:

- results in study withdrawal
- is associated with a serious adverse event
- is associated with clinical signs or symptoms
- leads to additional treatment or to further diagnostic tests
- is considered by the investigator to be of clinical significance

Serious Adverse Event

Adverse events are classified as serious or non-serious. A **serious adverse event** is any AE that is:

- fatal
- life-threatening
- requires or prolongs hospital stay
- results in persistent or significant disability or incapacity
- a congenital anomaly or congenital disability
- an important medical event

Important medical events are those that may not be immediately life-threatening but are clearly of major clinical significance. They may jeopardize the subject and require intervention to prevent the other serious outcomes noted above. For example, drug overdose or abuse, a seizure that did not result in an in-patient hospitalization, or intensive treatment of bronchospasm in an emergency department would typically be considered serious.

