All adverse events that do not meet any of the criteria for serious should be regarded as *nonserious adverse events*.

Adverse Event Reporting Period

The study period during which adverse events must be reported is typically defined as the period from the initiation of any study procedures to the end of the study treatment follow-up. For this study, treatment follow-up is described as approximately 16 weeks following the last administration of study treatment.

Stopping Rules

Infusion Stopping Rules

Study treatment infusion will be stopped if a least one of the following events occurs:

1. Allergic reaction as evidenced by severe dyspnea (defined as intense tightening of the chest, air hunger, breathlessness or feeling of suffocation), bronchospasm (defined as coughing, wheezing, difficulty breathing) or hypoxia (defined as pulse oximeter reading of less than 90%) after the product has been administered intravenously.
2. Hypersensitivity reactions such as rash, urticaria, itching, angioedema, nausea, vomiting, hypotension, or any evidence of anaphylaxis.
3. The patient verbally declines the treatment at any moment prior, or during the infusion.
4. Any febrile reaction will be an indicator for pausing the infusion for further evaluation.
5. Malignant Systolic blood pressure (SBP) greater than 170 and/or diastolic blood pressure greater than 100. SBP less than 80mm/Hg and/or DBP less than 40mm/Hg. *
6. Sudden Severe Hypotension (40 mm/Hg drop from infusion starting baseline) or systolic blood pressure <80mmHg.
7. Respiratory distress defined as having an acute sudden onset of shortness of breath or increased work of breathing, SaO₂ less than 90% or a respiratory rate >22 or < 10 breaths per minute. Any increased oxygen support that could indicate imminent respiratory failure.
8. Sudden increase or decrease in pulse rate of 30 bpm or more from infusion starting baseline or an absolute tachycardia of greater than 140 bpm or absolute bradycardia less than 45 bpm.
9. Change in neurologic status from infusion starting baseline including alertness.
10. The Principal Investigator may stop the infusion at any time, based upon PI's discretion.

*Any blood pressure from baseline exceeding or falling below $\pm 20\%$ of baseline or $\geq 140/90$ will necessitate a pause for evaluation.

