5.3.2.2. Adverse Events

AEs will be coded using the most recent version of the Medical Dictionary for Regulatory Activities (MedDRA).

A treatment emergent adverse event (TEAE) is defined as an event that has onset date on or after the first day of exposure to infusion treatment and on or before the last day of infusion treatment. Here the first day of exposure is defined as the first day of exposure to infusion treatment.

Treatment Adverse events (TAES) are summarised descriptively, whereas non-TEAEs are presented in listings. TAE data will be displayed in terms of the number of subjects with at least one event (N), percentage of subjects with at least one event (%) and the number of events (E).

Summaries of TAEs and of serious AEs will be presented as an overview including all AEs, serious AEs, AEs by severity, AEs by relation to treatment, action to AEs and treatment advised, and outcome of AEs.

Furthermore, summary tables based on system organ class and preferred terms are made for:

- All TAEs
- Serious AEs

Hope Biosciences Research Foundation HBPCOVID02

• AEs leading to withdrawal of study

Incidence and risk of AEs of special interest (includes serious or nonserious), including thromboembolic events, infections, and hypersensitivities will be summarized based on system organ class and preferred terms.

Individual adverse events will be listed.

The details of the planned displays are in programming specification document.

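### The SAP defines treatment-emergent events by onset date alone, and neither document says how to date an event that worsens after the first infusion

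*Protocol*

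**What the plan says.** The protocol brings worsening into the AE definition in two places. Under Adverse Event, an AE "is any symptom, sign, illness, or experience that develops or worsens in severity during the study". Under Physical Examinations, conditions diagnosed during screening "are not adverse events but are recorded as medical history", but if "any pre-existing conditions worsen during the trial, these must be recorded as adverse events". The Adverse Event Reporting Period runs "from the initiation of any study procedures to the end of the study treatment follow-up", with follow-up of about 16 weeks after the last administration.

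SAP 5.3.2.2 defines a TEAE as "an event that has onset date on or after the first day of exposure to infusion treatment", and no later than the last infusion day. Treatment adverse events are summarised, "whereas non-TEAEs are presented in listings". I read the SAP's TAE and TEAE as the same thing.

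SAP 7.2.2 also classifies by start date alone. As printed, it marks an event that starts before the first dose as treatment emergent (Y), and one that starts on or after it as not (N).

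TEAE incidence is among the primary endpoints in both documents.

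**The concern.** Every participant enters with at least one neurological symptom of at least 12 weeks' standing, continuous or relapsing (Inclusion Criterion 4). Aggravation of something already present is therefore a foreseeable form of harm, and the symptom itself began before dosing. A TEAE rule with no worsening limb can pass over that harm.

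Nothing else in the plan closes the gap. SAP 7.2.6 sets detailed rules for partial AE start dates but none for a worsened event. SAP 5.4 declares no departure from the protocol's analysis, so the narrower rule is not presented as a deliberate choice.

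At stake are the TEAE incidence, severity and relatedness summaries. Two sites of data entry, or two coordinators, could record the same clinical course differently, and one record would be tabulated while the other would not.

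**Working it through.** The documents give no figure to reproduce, so the check applies each written rule to hypothetical events.

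Inputs, counting the first infusion as day 0:
- Last infusion at Week 10 (Study Summary): 10 × 7 = day 70.
- End of study at Week 26: 26 × 7 = day 182.
- SAP 5.3.2.2: TEAE if 0 ≤ onset ≤ 70.
- SAP 7.2.2 as printed: Y if onset < 0. With the labels swapped: Y if onset ≥ 0.
- 5.3.2.2 plus a worsening limb, window unchanged: TEAE if 0 ≤ onset ≤ 70, or if onset < 0 and 0 ≤ worsening ≤ 70.

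| Event and how it is dated | 5.3.2.2 | 7.2.2 as printed | 7.2.2 swapped | 5.3.2.2 + worsening limb |
|---|---|---|---|---|
| Onset day −10, worsens day 20, onset date kept | No | Y | N | Yes |
| Same course, new record dated day 20 | Yes | N | Y | Yes |
| Onset day −10, worsens day 100, onset date kept | No | Y | N | No |
| Same course, new record dated day 100 | No | N | Y | No |

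Three results follow.

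1. Rows 1 and 2 are the same clinical course. Under 5.3.2.2 the dating convention alone decides whether it is a TEAE.
2. In every row, 7.2.2 as printed gives the opposite answer to 7.2.2 swapped, and in rows 1 to 3 it disagrees with 5.3.2.2. It does not rescue worsened events in any usable way, because it would also flag every pre-dose event that never worsens and reject every new event after dosing.
3. Rows 3 and 4 stay out of the TEAE tables even with a worsening limb, because the window shuts at day 70. That leaves (182 − 70)/7 = 16 of 26 weeks uncovered, or 16/26 = 62%.

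On size: suppose an arm has *n* pre-infusion events or conditions that worsen within the infusion period, and a fraction *q* of them keep the earlier date. The TEAE tables then hold (1 − *q*) × *n* of them. With *q* = 0 nothing is lost, and with *q* = 1 all are. The documents give neither *n* nor *q*. If blinding makes *q* equal in the two arms, the arm with more worsening loses more events.

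**The case against.** The other side has a substantial case.

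- **Most symptoms present at entry are medical history.** Their worsening must be recorded as an AE, and the natural date for that record is the date of worsening. SAP 5.3.2.2 then counts it if it falls in the infusion window. No passage tells sites to back-date. This stands, and it means that loss is possible but not certain. It does not remove the gap, because no passage tells sites to use the date of worsening either.
- **Few AEs may be open before dosing.** Table 1 schedules AE assessment only from Visit 2, the Visit 1 procedures include no AE step, and at Visit 2 AEs are assessed after the infusion. The earlier start of the reporting period is worded only as what is typical. This stands too. The more likely route is worsening of a pre-existing condition.
- **Other summaries may catch the event.** The summaries of serious AEs, AEs leading to withdrawal and AEs of special interest are not expressly limited to treatment-emergent events. This stands: the exposed group is non-serious worsening outside those summaries. The protocol itself notes that serious and severe differ, so a severe but non-serious worsening can be in this group.
- **The VAS and Fatigue Scale would show aggravation.** Only in part. They are collected at in-person visits and compared between arms, but this does not give AE incidence. The efficacy set is also limited to participants who received all four infusions.
- **A narrower SAP subset does not contradict a broader AE definition.** That is fair. The protocol names TEAEs without defining them, and the programming specification is not available. The point is an incomplete rule, not a contradiction between the two documents on this limb.

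**Conclusion.** The point holds as a gap in definition. The protocol counts worsening as an AE, the SAP's TEAE rule looks only at onset, and the dating of a worsened event is left open. Where the pre-infusion date is kept, non-serious worsening after the first infusion leaves the TEAE tables and appears only in listings. The conclusion assumes that the two documents are the whole rule and that no unseen specification or CRF guide settles the date.

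A reader might infer more, and the documents do not support it:

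- That such events *do* drop out. This happens only if the earlier date is kept, which is neither instructed nor excluded.
- That safety reporting as a whole misses them. The exposure concerns the TEAE tables.
- That the loss can be sized from the length of screening. The documents give no AE rate, no share of events that worsen and no dating practice, and Table 1 schedules no AE assessment at screening. No defensible figure can be given.

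It is worth settling before database lock, because it affects a primary safety endpoint and costs little.

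**What to change.** In SAP 5.3.2.2, define an AE as treatment emergent if it starts on or after the first infusion, or if it started earlier and increases in severity on or after the first infusion. Date the second kind at the increase, and tabulate its highest post-infusion severity. This applies equally to AEs already open and to pre-existing conditions. Put the same dating convention in the CRF completion instructions.

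Two repairs belong in the same edit:

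- **SAP 7.2.2.** Correct the Y/N flag so that it agrees with 5.3.2.2, and carry the worsening limb into it. Events with missing or partial dates now sit under N, so state where they should fall once the labels are corrected.
- **Window.** Reconcile the 5.3.2.2 window, which ends at the last infusion, with the protocol's reporting period. Otherwise worsening after the last infusion is still not counted.

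The cost is a few sentences in the SAP and the CRF instructions, with no new assessments. Keeping the convention there avoids a protocol amendment, which under Protocol Amendments would need an IND submission with FDA and IRB agreement. TEAE counts may rise slightly in both arms.
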